## Descriptive Analyses

The table of the number of acute migraine-specific medication days per month in the DBT analysis period is provided, and summarizes the parameter descriptively as a continuous variable by treatment group in each month of the DBT Phase and overall DBT.

## Treatment Group Comparisons

Treatment groups are compared using a linear mixed effects model with repeated measures and the following attributes:

- Variables: number of acute migraine-specific medication days per month as the dependent variable; treatment group, 4-level randomization stratum, categorical month (i.e., Months 1 to 3 of the DBT Phase), and the month-by-treatment group interaction as fixed effects
- Covariance structure for repeated measures accounting for within-subject correlated errors: see Section 6.3.1.3.

- SE estimation method: see Section 6.3.1.3.

The table displays the following model estimates:

- LSM, SE, and 95% CI by month and overall DBT for each treatment group
- Difference in LSMs between rimegepant and placebo (rimegepant – placebo), SE, 95% CI, and p-value at each month and overall DBT. Results support other secondary objective #3.

See Section 9.3.1 for example SAS code.

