**Figure 1 Study Schematic**

## 2.2 Treatment Assignment

The RTSM system assigns a subject identifier number at the Screening Visit.

The RTSM system randomizes eligible subjects to treatment groups (see Section 2.1) using permuted blocks of size 6 within each of the 4 randomization strata at the Baseline Visit. Randomization is stratified by (1) the number of migraine days reported to have occurred during the 28-day OP (4 to 7 or 8 to 14); and (2) the number of ROM medication categories with previous inadequate response (2 or 3 to 4).

The RTSM system also assigns specific container numbers for study drug to be dispensed at the Baseline Visit and subsequent visits in the DBT and OLE Phases.

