  - Migraine: subjects in the DBT efficacy analysis set with  $\geq 14$  days of eDiary efficacy data (not necessarily consecutive) in both the OP and  $\geq 1$  month (4-week interval) in the DBT Phase (see Section 6.3.1). This analysis set is used to assess migraine days, acute migraine-specific medication days, acute migraine medication days, and headache days.
  - First month migraine: subjects in the DBT efficacy analysis set with  $\geq 24$  days of eDiary efficacy data (not necessarily consecutive) in both the OP and in first month (4-week interval) of the DBT Phase (see Section 6.3.3.3). This analysis set is used to assess efficacy endpoints per week.
  - First week EOD treated migraine: subjects in the DBT efficacy analysis set with (1)  $\geq 24$  days of eDiary efficacy data (not necessarily consecutive) in the OP, (2) 7 consecutive days of eDiary efficacy data in the first week of the DBT Phase, and (2) EOD dosing in the first week of the DBT Phase (see Section 6.3.3.5). This analysis set is used to assess efficacy endpoints per day in the first week of the DBT Phase.

See Section 7.1 for derived dates and Section 7.2 for analysis periods.

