## Migraine-Related Event Days During the OP

The table of migraine-related event days per month during the OP is provided only for the migraine analysis set, and summarizes the following parameters descriptively as continuous or categorical variables during the OP analysis period:

- Migraine days per month by headache pain intensity (total; moderate or severe). Categories are  $<4$ ,  $\geq 4$  to  $<8$ ,  $\geq 8$  to  $<14$ ,  $\geq 14$ .
- Headache days per month by headache pain intensity (total; moderate or severe). Categories are same as for migraine days per month above.
- Acute migraine-specific medication days per month. Categories are 0,  $>0$  to  $<2$ ,  $\geq 2$  to  $<4$ ,  $\geq 4$  to  $<6$ ,  $\geq 6$  to  $<8$ ,  $\geq 8$  to  $\leq 14$ ,  $>14$ .
- Acute migraine medication days per month. Categories are same as for acute migraine-specific medication days per month above.

The table of migraine-related event days per week during the OP is provided only for the first month migraine analysis set, and summarizes the following parameters descriptively as continuous or categorical variables during the OP analysis period:

- Migraine days per week by headache pain intensity (total; moderate or severe). Categories are  $<1$ ,  $\geq 1$  to  $<2$ ,  $\geq 2$  to  $<3$ ,  $\geq 3$ .
- Headache days per week by headache pain intensity (total; moderate or severe). Categories are same as for migraine days per week above.

See Section 6.3.1 for migraine days per month, Section 6.3.3.1 for headache days per month, Section 6.3.3.3 for migraine days per week and headache days per week, Section 6.3.2.2 for acute migraine-specific medication days per month, Section 6.3.3.6 for acute migraine medication days per month, and Section 7.2 for the OP analysis period.

Categories may be redefined or combined based on the availability of the data.

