### 6.3.1 Primary Efficacy Endpoint

Subjects are instructed to report headache occurrence, headache pain features and associated symptoms, aura occurrence, and medication (i.e., triptan, ergotamine, lasmiditan, ubrogepant, or other) used to treat headache or aura in the eDiary headache report every day in the OP and DBT Phase.

Migraine days per month are assessed as “migraine days per 4 weeks” to correspond with the 4-week visit schedule. Migraine days per month are based on 4-week intervals, and are prorated to account for missing migraine reports.

See Section 9.2.2 for the definition of eDiary efficacy data days, and Section 9.2.5 for the definition of migraine days.

The number of migraine days per month in the DBT Phase is examined relative to the number of migraine days per month in the OP for the migraine analysis set, i.e., subjects with  $\geq 14$  days of eDiary efficacy data in both the OP analysis period and  $\geq 1$  month (i.e., 4-week interval) in the on-DBT efficacy analysis period.

Months in the DBT Phase are defined as follows:

- Month 1:  $\leq 4$  weeks; study days 1 to 28
- Month 2:  $>4$  to  $\leq 8$  weeks; study days 29 to 56
- Month 3:  $>8$  to  $\leq 12$  weeks; study days 57 to 84.

Analyses are based on eDiary efficacy data dates in the OP and on-DBT efficacy analysis periods.

The number of migraine days per month is prorated to 28 days and derived as follows:

- OP:  $28 \times (\text{total number of migraine days in the OP analysis period}) / (\text{total number of eDiary efficacy data days in the OP analysis period})$ . Subjects must have  $\geq 14$  days of eDiary efficacy data (not necessarily consecutive) in the OP to be evaluable.
- Month (i.e., 4-week interval) in the on-DBT efficacy analysis period:  $28 \times (\text{total number of migraine days in the month}) / (\text{total number of eDiary efficacy data days in the month})$ .

Subjects must have  $\geq 14$  days of eDiary efficacy data (not necessarily consecutive) in the specified month to be evaluable.

- Overall DBT:  $28 \times (\text{total number of migraine days through Month 3 in the on-DBT efficacy analysis period}) / (\text{total number of eDiary efficacy data days through Month 3 in the on-DBT efficacy analysis period})$ .

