### 6.3.2.2 *Acute Migraine-Specific Medication Days per Month Over Time on DBT*

Acute migraine-specific medication days per month are assessed as “acute migraine-specific medication days per 4 weeks” to correspond with the 4-week visit schedule. Acute migraine-specific medication days per month are based on 4-week intervals, and are prorated to account for missing migraine reports. See Section 9.2.4 for the definition of acute migraine-specific medication days.

Analyses are based on the migraine analysis set with eDiary efficacy data dates in the on-DBT efficacy analysis period.

The number of acute migraine-specific medication days per month in the DBT Phase are prorated to 28 days and derived as follows:

- Month (i.e., 4-week interval) in the on-DBT efficacy analysis period:  $28 \times (\text{total number of acute migraine-specific medication days in the month}) / (\text{total number of eDiary efficacy data days in the month})$ . Subjects must have  $\geq 14$  days of eDiary efficacy data (not necessarily consecutive) in the specified month to be evaluable.
- Overall DBT:  $28 \times (\text{total number of acute migraine-specific medication days through Month 3 in the on-DBT efficacy analysis period}) / (\text{total number of eDiary efficacy data days through Month 3 in the on-DBT efficacy analysis period})$ .

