### **Treatment Group Comparisons**

Treatment groups are compared using a model with the same properties as the model specified in Section 6.3.2.2, except that the number of acute migraine medication days per month is the dependent variable. The corresponding table has the same format. Results support exploratory objective #7.

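### The two acute-medication-day models leave out the Observation Phase value of their own outcome, a precision loss that can be avoided at almost no cost

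*SAP*

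**What the plan says.** Other secondary objective 3 concerns the mean number of acute migraine-specific medication days per month on double-blind treatment (DBT). For it, SAP 6.3.2.2 fits a repeated-measures linear model with "number of acute migraine-specific medication days per month as the dependent variable; treatment group, 4-level randomization stratum, categorical month" and the month-by-treatment interaction. The outcome is a 28-day rate: the SAP says the days "are prorated to account for missing migraine reports". No OP term appears.

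For exploratory objective 7, SAP 6.3.3.7 states: "Treatment groups are compared using a model with the same properties as the model specified in Section 6.3.2.2". Only the outcome is swapped, for the broader medication-day variable. The omission therefore carries over.

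The missing information is on hand:

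- SAP 6.3.1 has subjects report medication "used to treat headache or aura in the eDiary headache report every day in the OP and DBT Phase".
- SAP 6.2.5.2 tabulates OP medication days per month for the migraine analysis set, the set used in both models. The entry reads "Acute migraine-specific medication days per month. Categories are 0", and the classes run up to more than 14. The broader medication-day variable is tabulated the same way.
- SAP 4.1 admits a subject to that set only with at least 14 "days of eDiary efficacy data (not necessarily consecutive) in both the OP and" at least one DBT month, so every analysed subject has a usable OP value.

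**The concern.** Every other modelled continuous endpoint in the SAP uses its own baseline. Migraine days and headache days, monthly and weekly, are analysed as change from the OP (6.3.1.3, 6.3.3.1, 6.3.3.3). MSQ, MIBS, MFIQ, WPAI, PGA and HIT-6 carry the baseline score as a covariate (6.5.1 to 6.5.6). The two medication-day models are the exception, and no reason is given.

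The stratum is a thin substitute. A migraine-specific medication day requires a triptan, ergotamine, lasmiditan or ubrogepant (SAP 9.2.4). Protocol Appendix 4 also permits NSAIDs, acetaminophen and other agents. A subject with many migraine days who treats only with an NSAID scores zero on this outcome; another with the same number who always takes a triptan scores high. Both can sit in the same stratum. That difference existed before randomisation, was measured before randomisation, and is left in the residual.

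What is at stake is the width of the confidence intervals that SAP 6.3.2.2 and 6.3.3.7 will report for the treatment difference.

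**Working it through.** **1. The plan's own figure.** SAP section 5 gives a power statement for the primary endpoint only: difference 1.0 day, SD 3.6 days, about 280 analysed per group, two-sided alpha 0.05. SE = 3.6 × √(2/280) = 0.304; 1.0/0.304 = 3.29; Φ(3.29 − 1.96) = 0.908. The stated figure of roughly 90% is reproduced. No SD, correlation or power is given for the medication-day endpoints, so the rest needs an assumption.

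**2. Gain from the covariate.** Let r be the correlation between OP and on-treatment medication days, given stratum. Adding the OP value multiplies the residual variance by (1 − r²) and the SE by √(1 − r²). With 280 per group, the equivalent unadjusted number is 280/(1 − r²). The power column takes a difference that the planned model detects with 80% power: Φ[(1.96 + 0.842)/√(1 − r²) − 1.96].

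| r (assumed) | Variance cut, r² | SE ratio | SE cut | 280 per group worth | 80% power becomes |
|---|---|---|---|---|---|
| 0.3 | 9% | 0.954 | 5% | 308 | 83.6% |
| 0.4 | 16% | 0.917 | 8% | 333 | 86.4% |
| 0.5 | 25% | 0.866 | 13% | 373 | 89.9% |
| 0.6 | 36% | 0.800 | 20% | 438 | 93.8% |
| 0.7 | 49% | 0.714 | 29% | 549 | 97.5% |

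**3. How much the stratum might already capture.** A simulation for the migraine-specific outcome used invented inputs:

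- 4 to 14 OP migraine days
- 50%, 70% or 90% of subjects ever using a migraine-specific drug
- users treating on average 60% of migraine days, with the same personal habit in both periods
- latent migraine frequency correlated 0.3 or 0.6 between periods
- a second stratification factor unrelated to the outcome.

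The stratum explained under 3% of outcome variance. The partial r was 0.52 to 0.79 and the SE ratio 0.61 to 0.86. This shows that a large gain is plausible if habit is stable. It is not evidence about this trial, because stable habit and an uninformative second factor were built in.

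**4. Chance imbalance.** With 280 per group, the OP means differ by more than 1.96 × √(2/280) = 0.166 SD in 1 trial in 20. At r = 0.6 and equal OP and DBT SDs, a difference of that size moves the unadjusted estimate by 0.6 × 0.166 = 0.10 SD. For scale, the primary endpoint's planned effect is 1.0/3.6 = 0.28 SD. This variation is already contained in the unadjusted SE; the covariate removes it.

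**5. Covariate or change from OP.** With equal variances in the two periods, a change score has variance 2(1 − r) relative to the on-treatment value: 1.4 at r = 0.3, 1.0 at 0.5, 0.6 at 0.7. It helps only above r = 0.5 and does harm below. The covariate form does not carry that risk.

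**The case against.** The best defence is that the model follows the endpoint as defined. Protocol 3.2.2 and SAP Table 3 ask for a mean number of days, not a change, and the objective is worded as an evaluation rather than a comparison. SAP section 5 places other secondary and exploratory endpoints outside the hierarchy, with descriptive p-values and no power claim. No rule in the documents is broken. All of this stands and limits the consequence. It does not argue against the covariate, which leaves the endpoint as it is.

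Three stronger readings are tempting, and the documents do not support them.

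- A reader might infer that the models analyse raw counts with no baseline adjustment at all. The outcome is prorated to 28 days, and the stratum carries dichotomised OP migraine days. Medication-specific days are a subset of migraine days (SAP 9.2.4), so the stratum is a related variable, though probably a weak proxy.
- A reader might infer that the loss of precision is known to be large. Without an SD or an OP-to-DBT correlation for these endpoints, it cannot be called more than probable. At r = 0.3 it is only 5% of the SE. Nor need r be the same for both: the broader endpoint also counts migraine days treated with any other medication (SAP 9.2.3), so it may follow migraine days, and hence the stratum, more closely.
- A reader might infer that an OP imbalance would bias the result. Randomisation makes the unadjusted comparison unbiased, its SE allows for chance imbalance, and the baseline table by treatment group would show one.

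**Conclusion.** The omission is certain from the text; its size is not. Both models could use an OP value that is collected daily and available for every analysed subject, and they do not. On the assumption that r lies between 0.3 and 0.7, adjustment would cut the SE by 5% to 29% and the residual variance by 9% to 49%. This is a precision improvement for other secondary objective 3 and exploratory objective 7, not a validity error. No primary or key secondary conclusion depends on it.

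**What to change.** In SAP 6.3.2.2, define OP acute migraine-specific medication days per month as 28 × (medication days in the OP analysis period) / (eDiary efficacy data days in the OP analysis period), matching the OP formula for migraine days in 6.3.1, and add it to the model as a continuous covariate. In 6.3.3.7, do the same with OP acute migraine medication days per month. Keep the on-treatment number as the dependent variable and change nothing else.

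The cost is one formula and one covariate per model. The formula has to be written out: 6.2.5.2 refers to 6.3.2.2 for the derivation, but 6.3.2.2 covers only the DBT months and overall DBT. For the broader variable, 6.2.5.2 points to 6.3.3.6, which is the time-to-event section; this should read 6.3.3.7.

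No subject is lost. Protocol 9.3.1.2 sets no model for these endpoints and Protocol section 9 lets the SAP modify methods, so a SAP amendment should be enough. It should be made before unblinding at the primary completion database lock.

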### 6.3.2.3 Overall Summary of Primary and Key Secondary Endpoints in Hierarchical Testing

The overall summary table of treatment comparisons of all primary and key secondary endpoints tested hierarchically displays the following statistics:

- Continuous endpoints involving change from OP or baseline
  - n (i.e., number of subjects in the analysis set), LSM change, and 95% CI for each treatment group
  - Difference in LSM changes between rimegepant and placebo, 95% CI, and p-value.

This applies to the primary endpoint and the following key secondary efficacy and outcomes research endpoints: mean change in number of migraine days per month in the first month of the DBT Phase (see main analysis in Section 6.3.1.3); mean change in number of migraine days per month in the last month of the DBT Phase (see main analysis in Section 6.3.1.3); MSQ restrictive role domain score mean change from baseline at Week 12 (see Section 6.5.1); and MIBS score mean change from baseline at Week 12 (see Section 6.5.2).

- Binary endpoints
  - Response rate (“n/N” and percentage) and 95% CI for each treatment group
  - Stratified percentage difference between rimegepant and placebo, 95% CI, and p-value.

This applies to the key secondary efficacy endpoint of percentage of subjects with  $\geq 50\%$  reduction in number of moderate or severe migraine days per month in the last month of the DBT Phase (see Section 6.3.2.1).

Endpoints are displayed in the order presented in Sections 3.2.1 and 3.2.2.1. P-values that are determined to be significant based on the testing hierarchy are flagged.

If the main analysis of the primary endpoint is significant (i.e.,  $p\text{-value} \leq 0.05$ ; see Section 6.3.1.3), then the key secondary efficacy and outcomes research endpoints are tested hierarchically, each at a 2-sided alpha level of 0.05, in the order specified in Section 3.2.2.1. Thus, a key secondary endpoint is tested only if the preceding key secondary endpoint in the hierarchy is determined to be significant (i.e.,  $p\text{-value} \leq 0.05$ ). If a test in the hierarchy is not significant, then any further tests on endpoints in the sequence have p-values presented only for descriptive purposes, and no conclusions are drawn from those results.

If the main analysis of the primary endpoint is not significant (i.e.,  $p\text{-value} > 0.05$ ), then any further tests of key secondary endpoints will have  $p$ -values presented only for descriptive purposes, and no conclusions are drawn from those results.

For a given treatment group comparison of a continuous endpoint, the null hypothesis of interest  $H_0$  is that the mean change observed on rimegepant (denoted  $\mu_{\text{rimegepant}}$ ) is equal to the one observed on placebo (denoted  $\mu_{\text{placebo}}$ ), i.e.,  $H_0: \mu_{\text{rimegepant}} = \mu_{\text{placebo}}$ . The alternative 2-sided hypothesis of interest  $H_1$  is that the mean changes observed on rimegepant and placebo differ, i.e.,  $H_1: \mu_{\text{rimegepant}} \neq \mu_{\text{placebo}}$ . For a given treatment group comparison of a binary endpoint, the hypotheses are based on percentages instead of mean changes.

The overall summary table of treatment comparisons of all primary and key secondary efficacy endpoints during the DBT Phase is also produced by subgroup level for all efficacy subgroups of interest described in Section 4.3. Separate tables are provided for each subgroup. Analyses of continuous endpoints are performed using models that exclude randomization stratum as a fixed effect, while analyses of binary endpoints are performed unstratified.  $P$ -values are presented only for descriptive purposes, and are not flagged for significance.

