3.2. Secondary Endpoints

3.2.1. Key Secondary Endpoints

1. Proportion of subjects with $\geq 50\%$ reduction from the Observation Phase in the number of migraine days of moderate or severe headache pain intensity per month over the entire DBT Phase (Weeks 1 to 12).
2. Mean change from the Observation Phase in the number of migraine days per month in the first 4 weeks (Weeks 1 to 4) of the DBT Phase.
3. Mean change from the Observation Phase in the number of migraine days per month in the last 4 weeks (Weeks 9 to 12) of the DBT Phase.
4. Mean change from baseline in the MSQ restrictive role function domain score at Week 12 of the DBT Phase.
5. Mean change from baseline in the MIBS score at Week 12 of the DBT Phase.

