9.3.1.2. Secondary Endpoints

The proportion of subjects with $\geq 50\%$ reduction from the Observation Phase in the number of migraine days of moderate or severe headache pain intensity per month over the entire DBT Phase (Weeks 1 to 12) will be assessed using Mantel-Haenszel risk estimation with stratification by randomization stratum for the DBT migraine analysis set. Missing data are imputed as non-response (i.e., failure). The difference estimate (rimegepant – placebo), SE, p-value, and 95% CI will be reported.

The mean change from the Observation Phase in the number of migraine days per month in the first 4 weeks (Weeks 1 to 4) of the DBT Phase will be assessed for the DBT migraine analysis set from the same model used for the primary endpoint.

The mean change from the Observation Phase in the number of migraine days per month in the last 4 weeks (Weeks 9 to 12) of the DBT Phase will be assessed for the DBT migraine analysis set from the same model used for the primary endpoint.

The mean changes from baseline in MSQ restrictive role function domain score and MIBS score at Week 12 will be assessed for the DBT efficacy analysis set using a linear mixed effects model with repeated measures that will include the following variables: change from baseline in the score as the dependent variable; baseline score as a covariate; and fixed effects for treatment group, randomization stratum, week, and week-by-treatment group interaction. Weeks are 4, 8, and 12. The Week 12 difference estimate (rimegepant – placebo),

SE, 95% CI, and p-value will be reported for each endpoint. The Huber-White "sandwich" estimator will be used for the estimation of SEs.

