**Table 2 Key Secondary Objective Estimands**

Objective 1	Proportion of subjects with <math>\geq 50\%</math> reduction from the OP in the number of moderate or severe migraine days per month over the entire DBT Phase
Efficacy Endpoint	Proportion of subjects with $\geq 50\%$ reduction from the OP in number of moderate or severe migraine days per month over the entire DBT Phase (Weeks 1 to 12)
Summary	Percentage of subjects by treatment group, and difference in percentages between treatment groups using Mantel-Haenszel risk estimation for the migraine analysis set
Intercurrent Events	Study drug discontinuation: composite strategy Nonstudy prophylactic migraine medication use: treatment policy strategy Nonstudy acute migraine-specific medication use: composite strategy Use of nonstudy other medication to treat headache (migraine or nonmigraine) or aura: treatment policy strategy
Objective 2	Mean reduction from the OP in the number of migraine days per month in the first 4 weeks of the DBT Phase
Efficacy Endpoint	Mean change from the OP in the number of migraine days per month in the first 4 weeks (Weeks 1 to 4) of the DBT Phase
Summary	Mean change from the OP by treatment group using descriptive statistics and linear mixed effects model with repeated measures, and difference in mean changes between treatment groups from model for the migraine analysis set
Intercurrent Events	Study drug discontinuation: hypothetical strategy Nonstudy prophylactic migraine medication use: treatment policy strategy Nonstudy acute migraine-specific medication use: composite strategy

	Use of nonstudy other medication to treat headache (migraine or nonmigraine) or aura: treatment policy strategy
Objective 3	Mean reduction from the OP in the number of migraine days per month in the last 4 weeks of the DBT Phase
Efficacy Endpoint	Mean change from the OP in the number of migraine days per month in the last 4 weeks (Weeks 9 to 12) of the DBT Phase
Summary	Mean change from the OP by treatment group using descriptive statistics and linear mixed effects model with repeated measures, and difference in mean changes between treatment groups from model for the migraine analysis set

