### Treatment Group Comparisons

For each pain intensity (total; moderate or severe) and select percentage reduction ( $\geq 30\%$ ,  $\geq 50\%$ ,  $\geq 75\%$ , and  $100\%$ ), the percentages of subjects with reductions from the OP in the number of migraine days per month are compared between rimegepant and placebo using Mantel-Haenszel risk estimation (e.g., SAS proc strdate) with stratification by 4-level randomization stratum. Percentages are calculated against the number of subjects in the migraine analysis set at all time points.

The table displays the following statistics at each month of the DBT Phase and overall DBT by headache pain intensity:

- Response rate (i.e., “n/N” and percentage), ASE, and 95% CI for each treatment group
- Stratified percentage difference between rimegepant and placebo (rimegepant – placebo), ASE, 95% CI, and p-value.

Results for the endpoint of  $\geq 50\%$  reduction of moderate or severe pain intensity in the overall DBT support key secondary objective #1. Results for all other endpoints support exploratory objective #2.

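### SAP 6.3.2.3 places key secondary endpoint 1 in the last month of double-blind treatment, contradicting the Weeks 1 to 12 definition in the protocol and the rest of the SAP

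*SAP*

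**What the plan says.** Protocol 3.2.1 defines key secondary endpoint 1 as the proportion of subjects with at least a 50% reduction in "migraine days of moderate or severe headache pain intensity per month over the entire DBT Phase (Weeks 1 to 12". Protocol 9.3.1.2 gives the analysis for the same window: "per month over the entire DBT Phase (Weeks 1 to 12) will be assessed using Mantel-Haenszel risk estimation". Table 2 of the SAP (Section 3.2.2.1) repeats the definition: "reduction from the OP in number of moderate or severe migraine days per month over the entire DBT Phase (Weeks 1 to 12".

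SAP 6.3.2.1 links results to objectives. The 50% or greater "reduction of moderate or severe pain intensity in the overall DBT support key secondary objective #1", and the section adds: "Results for all other endpoints support exploratory objective #2". Response in a single month is therefore exploratory.

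SAP 6.3.2.3 specifies the summary table for hierarchical testing. Under binary endpoints it says that the statistics apply to the percentage of subjects with a 50% or greater "reduction in number of moderate or severe migraine days per month in the last month of the DBT Phase (see Section 6.3.2.1". The same section says that the key secondary endpoints are "tested hierarchically, each at a 2-sided alpha level of 0.05, in the order specified in Section 3.2.2.1", and that "a key secondary endpoint is tested only if the preceding key secondary endpoint in the hierarchy is determined to be significant".

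**The concern.** Key secondary endpoint 1 is the step directly after the primary. If its p-value exceeds 0.05, endpoints 2 to 5 become descriptive: migraine days in the first and last 4 weeks, MSQ restrictive role function, and MIBS. Section 6.3.2.3 specifies the table in which p-values are flagged as significant under the hierarchy, so a wrong window in that section matters more than a slip in background text.

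The two windows also carry different missing-data rules, so the difference is more than a label. A program written from the literal words would put an exploratory result in a confirmatory position and open or close the rest of the sequence on it.

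**Working it through.** **The plan's own figure.** The only stated power is for the primary endpoint (Protocol 9.1, SAP 5): 280 per group, difference 1.0 day, SD 3.6, two-sided alpha 0.05. The standard error is 3.6 × √(2/280) = 0.304. Then 1.0/0.304 = 3.287, 3.287 − 1.960 = 1.327, and Φ(1.327) = 0.908. With the noncentral t the result is 0.907. The stated figure of roughly 90% reproduces, and this point does not affect it.

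**The definitions side by side.**

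| Place | Window for key secondary 1 |
|---|---|
| Protocol synopsis, 2.2.1, 3.2.1 | Entire DBT Phase, Weeks 1 to 12 |
| Protocol 9.3.1.2 (analysis) | Entire DBT Phase, Weeks 1 to 12 |
| SAP 3.1.2.1 | Entire DBT Phase, Weeks 1 to 12 |
| SAP 3.2.2.1, Table 2 | Entire DBT Phase, Weeks 1 to 12 |
| SAP 6.3.2.1 | Overall DBT; all other results exploratory |
| SAP 6.3.2.3 | Last month of the DBT Phase |

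SAP 5 and SAP 6.3.2.3 both take the testing order from 3.2.2.1, and the phrase at issue cites 6.3.2.1. Section 6.3.2.3 therefore contradicts its own cross-references. It is current text. The Revision History entries that name 6.3.2.3 (Versions 3 and 6) record no change of window.

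**The missing-data rules (SAP 6.3.2.1).** For a single month, a subject without at least 14 diary days in that month is a failure. For the overall DBT there is no minimum per month beyond membership of the migraine analysis set, which needs 14 days in at least one DBT month. Month 3 is study days 57 to 84 (SAP 6.3.1), and on-DBT efficacy data stop no later than one day after the last double-blind dose (SAP 7.2). Fourteen days from Day 57 run to Day 70, since 57 + 13 = 70, so the last dose must fall on Day 69 or later. A subject who stops before Day 69 fails automatically on the last-month version but can still be a responder over Weeks 1 to 12.

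**Whether the two versions lead to the same decision.** The documents give no responder rates, so every input here except the 280 per group is an assumption: mean about 7 baseline days; 5% or 15% of subjects with Month 1 data only; one migraine-day count, not split by intensity; an unstratified two-sample test in place of the stratified Mantel-Haenszel analysis; 2,000 runs per row. The table shows how often one version reached p ≤ 0.05 and the other did not.

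| Assumed effect in Months 1, 2, 3 (days) | 5% with Month 1 only | 15% with Month 1 only |
|---|---|---|
| 1.0, 1.0, 1.0 (constant) | 13.4% | 19.4% |
| 1.4, 1.0, 0.6 (fading) | 53.8% | 57.0% |
| 0.6, 1.0, 1.4 (growing) | 4.0% | 7.0% |
| 0, 0, 0 (none) | 7.8% | 8.2% |

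The simulation error is at most about 1.1 percentage points, from √(0.57 × 0.43/2000) = 0.011. With no effect, each version alone rejected in about 5% of runs (5.4% and 4.8% in the first column; 5.0% and 5.6% in the second).

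**The case against.** The strongest reply is that the hierarchy already resolves to Weeks 1 to 12. SAP 5, which governs type 1 error, takes its order from 3.2.2.1. Section 6.3.2.3 does the same and cites 6.3.2.1, and all of these lead to the entire DBT Phase. A programmer who follows the cross-references would run the right analysis. The stray words may have been carried over from key secondary endpoint 3, listed in the same section, where the last month is correct. This stands, and it is why the harm is conditional.

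Four stronger readings are tempting but not supported:

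- A reader might infer that the SAP has changed the endpoint. One phrase that conflicts with its own citations, with no such entry in the Revision History, does not show that.
- A reader might infer that last-month response is not pre-specified at all. It is, under exploratory objective 2; it is not pre-specified as a step in the hierarchy.
- A reader might infer that type 1 error is lost, or that the endpoint will be chosen after unblinding. Either version controls error if it is the one fixed in advance. SAP 2.3 also has draft tables produced with dummy treatment groups before the PCD lock, and SAP 6.1.1 places the templates in a separate mock document.
- A reader might want one figure for lost power. Without responder rates, any such figure reflects the chosen inputs.

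The reply does not make the correction unnecessary. Protocol 9 lets the SAP modify the protocol and requires an amendment only for major changes to the primary endpoint definitions or their analyses. The protocol's definition of a key secondary endpoint therefore does not automatically override the SAP text.

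**Conclusion.** The contradiction is real and is wrong as written: the section that decides which p-values are flagged names a different window for key secondary endpoint 1 from every other place that defines it. It is most likely a drafting error. The consequence arises only if the table is programmed from the literal wording; in that case an exploratory endpoint, with automatic failure for subjects lacking 14 diary days in Month 3, would control access to endpoints 2 to 5.

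The textual finding needs no assumptions. The simulated disagreement of roughly 4% to 57% depends on the assumed responder pattern and mainly on how the effect changes over time. It supports only the statement that the two versions cannot be swapped. Because the phrase affects the first step after the primary and costs almost nothing to correct, it should be corrected before the PCD lock.

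**What to change.** In SAP 6.3.2.3, for the binary endpoint only, change the window from the last month to the entire DBT Phase (Weeks 1 to 12). State there that the flagged p-value is the overall-DBT Mantel-Haenszel result, stratified by the 4-level randomization stratum, from 6.3.2.1.

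Keep the last-month wording for the mean change in migraine days (key secondary endpoint 3), where it is correct.

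Check that the mock table document, which was not available here and may already be right, and the subgroup summary shells use the same window. For the subgroup tables this is a consistency edit only, since their p-values are descriptive and not flagged.

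The cost is one phrase and one sentence in the SAP, plus a check of the shells. Sample size, data collection and analysis method are unchanged.
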